 - After the PENG block is placed, patients will have THA under spinal or general anesthesia. Spinal anesthesia will be provided by intrathecal injection of hyperbaric (0.75%) bupivacaine. General anesthesia will be provided by propofol induction, rocuronium for muscle relaxation and inhalation anesthetics for maintenance. Patients will receive fentanyl 25-50 mcg iv for increase in systolic blood pressure (SBP) > 25% of baseline SBP. Intraoperatively patients will also receive 4mg dexamethasone iv and 4 mg ondansetron iv.
 - Control group participants will be transferred to the block area preoperatively, and care will proceed as if they were receiving injection.
 - Patients will be placed in the supine position resting comfortably. Standard noninvasive monitors will be applied, and oxygen will be administered via nasal cannula. Parenteral midazolam and fentanyl will be titrated to patient comfort. Standard skin sterilization, prepping and draping will be applied to the area. The ultrasound probe will be used to

identify the iliopubic eminence (IPE). Only skin will be numbed using 2-3 cc of 2% lidocaine and NO bolus of bupivacaine will be injected.

- Postoperative patients in both the PENG arm and the control arm will be given scheduled PO acetaminophen 975 mg BID, and celecoxib 200mg BID (Dose of celecoxib will be adjusted based on renal function, and no celecoxib will be given for GFR < 30 ml/min) as part of multimodal pain regimen. Patients will be given a standard pain regimen of PRN Oxycodone 5 mg Q 4 hours for breakthrough pain, and hydromorphone 1mg IV every 6 hours prn as rescue analgesia for severe pain (NRS score more than 7/10). Patients will get prn ondansetron 4 mg iv every 4 hours. Naloxone iv prn will be used for any opioid related itching or respiratory depression.
- The following data will be collected
 - Quality of recovery (QoR) survey will be filled on post-operative day at 24 and 48 hours.
 - Patients will be evaluated immediately post-operatively in PACU, and 6, 12 and 24 hours post-surgery to determine VAS pain scores at rest and movement on the scale of 0-10. Also highest pain score during first 24 hours will be recorded.
 - Twenty-four hour opioid consumption will be calculated with respect to 24 hours oxycodone use and 24 hours hydromorphone use.
 - Data for postoperative use of ondansetron and naloxone will be collected. Also any postoperative episodes of nausea, vomiting, and itching will also be recorded.

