9.0 STATISTICAL CONSIDERATIONS

General Data Analysis Plan:

The distribution of the continuous factors will be examined using data visualization techniques such as q-q plots and the Shapiro-Wilk test. All normally distributed demographic and continuous variables will be expressed as means and standard deviations; categorical factors will be expressed as proportions. For non-normal data, the medians and inter quartile ranges will be displayed. For data that are normally distributed, Student's t-test will be used to compare the groups. For data that are not normally distributed, a Mann-Whitney tests will be used for comparisons. Chi-square or Fisher's exact tests will be used to analyze categorical data. Time to event data such as distance of first ambulation will be analyzed using Kaplan-Meier curves. The planned sub-group analysis will be conducted for GA vs. Spinal using a 2x2 ANOVA test. For all comparisons, a value of $p < 0.05$ will be considered statistically significant. Statistical analyses will be performed using SAS for Windows, version 9.2.

Statistical Power and Sample Size Estimates: Fifty-six patients in each group are required to detect a Minimal Clinically Important Difference (MCID) of 8 points for QoR-15 score assuming a standard deviation of 15 points using data from previous studies (19, 20) for 5% significance level and 80% power.

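### Immediate PACU pain and intraoperative opioid are compared without accounting for spinal versus general anaesthesia; if spinal leaves most patients near zero, the pooled test is valid but loses much of its power

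*Combined protocol and SAP*

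**What the plan says.** Section 6.0 (Study Interventions/Procedures) leaves the anaesthetic open: "patients will have THA under spinal or general anesthesia". Spinal is given with intrathecal bupivacaine. Intraoperative opioid follows a blood-pressure trigger that does not distinguish between anaesthetics: "Patients will receive fentanyl 25-50 mcg iv for increase in systolic blood pressure (SBP) > 25% of baseline SBP". Pain is scored as follows: "Patients will be evaluated immediately post-operatively in PACU, and 6, 12 and 24 hours post-surgery to determine VAS pain scores at rest and movement". The measured outcomes in the same section list immediate postoperative VAS and intraoperative opioid consumption as secondary.

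Section 5.0 randomises 1:1 in permuted blocks of varying size and names no stratification factor.

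Section 9.0 (Statistical Considerations) uses a t-test for normal data. Otherwise: "For data that are not normally distributed, a Mann-Whitney tests will be used for comparisons". It also plans a sub-group analysis of general versus spinal anaesthesia by 2x2 ANOVA, without naming an outcome. The Statistical analysis text that follows the QoR-15 form has the same t-test or rank-sum choice, without stratification, and does not mention the sub-group analysis. Anaesthetic type is not in the list of variables to be collected.

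**The concern.** These two outcomes are the ones most exposed to the anaesthetic itself. A spinal may still be acting when the patient reaches recovery, and it may make the blood-pressure trigger for fentanyl less frequent. If so, spinal patients sit at or near zero in both arms and tell us little about the block. A pooled ranking then mostly separates spinal from general patients, and that separation acts as noise in the comparison of PENG with control.

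Analgesic efficacy is part of the second study objective. The risk is that a real effect in general-anaesthesia patients is reported as no difference in PACU pain, or as no intraoperative opioid sparing.

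**Working it through.** **1. The plan's own figure.** Section 9.0 states: "Fifty-six patients in each group are required", for a "Minimal Clinically Important Difference (MCID) of 8 points for QoR-15 score", "assuming a standard deviation of 15 points", "for 5% significance level and 80% power". With a two-sided test (sidedness is not stated), n = 2(1.96 + 0.84)² × 15² / 8² = 2 × 7.849 × 225 / 64 = 55.2, so 56 per arm. This reproduces. It covers QoR-15 at 24 hours only; no power is stated for PACU pain or intraoperative opioid.

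**2. Why pooling dilutes.** Take 112 patients, half under spinal and all of those at zero, with no ties among the rest. Spinal patients share mean rank 28.5; general patients hold ranks 57 to 112, mean 84.5. The overall mean is 56.5.
- Between-anaesthetic variance of the ranks: 28² = 784.
- Within-anaesthetic variance: half of (56² − 1)/12 = 261.25, which is 130.6.
- Share due to anaesthetic: 784 / (784 + 130.6) = 86%.

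The unstratified test carries that 86% as noise.

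**3. The two tests.** In stratum s, with m PENG patients, k controls and N = m + k:
- U_s = PENG rank sum − m(N + 1)/2
- V_s = [mk / (N(N − 1))] × Σ(r − (N + 1)/2)²

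The pooled test is U/√V with everyone in one stratum. The van Elteren (stratified Wilcoxon) test is Σ[U_s/(N_s + 1)] / √Σ[V_s/(N_s + 1)²], over general and spinal.

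**4. Power if spinal patients are mostly at zero.** Assumptions, none from the documents: 56 per arm; general-anaesthesia VAS 5 v 3, SD 2.5; 80% of spinal patients at zero in both arms. For fentanyl: mean 2 v 1.2 doses under general anaesthesia, and 5% of spinal patients treated. The figures are simulated; repeat runs agree within a few points.

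| Spinal share | VAS pooled | VAS van Elteren | VAS additive model | Fentanyl pooled | Fentanyl van Elteren |
|---|---|---|---|---|---|
| 30% | 65% | 87% | 92% | 51% | 74% |
| 50% | 30% | 62% | 77% | 24% | 54% |
| 60% | 20% | 45% | 61% | 19% | 43% |
| 70% | 12% | 29% | 48% | 12% | 30% |

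The additive model is a linear model with arm and anaesthetic and no interaction. Type I error was about 4-6% for all three methods. At lower spinal shares the loss for VAS is smaller: 92% v 97% at 10% spinal and 80% v 93% at 20%.

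**5. A second set of inputs.** Here the general-anaesthesia effect is 8/15 = 0.53 SD (mean 5, SD 2), which gives about 77% power if no one has a spinal. With every spinal patient at zero, PACU pain has 34% pooled v 64% stratified at 25% spinal, and 12% v 47% at 50%.

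**6. Power if spinal patients are not near zero.** Same inputs as step 5, pooled v van Elteren:

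| Spinal patients | 25% spinal | 50% spinal |
|---|---|---|
| Mean 2, SD 2, no block effect | 46% v 51% | 21% v 26% |
| Mean 3, SD 2, half effect | 61% v 66% | 47% v 53% |
| Mean 3, SD 2, full effect | 72% v 77% | 66% v 75% |

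With the step 4 effect and spinal patients at mean 2, SD 2 and no effect, the figures are 77% v 78% at 30% spinal, 48% v 52% at 50%, and 31% v 32% at 60%.

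**The case against.** The strongest reply is that the premise is not in the documents. They give no spinal share, no PACU scores under spinal and no expected fentanyl use by anaesthetic. A reader might infer that spinal is known to hold both outcomes near zero, so that the plan halves its power. That is an assumption, and step 6 shows the loss is small when it fails. This stands.

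Second, a reader might infer that the pooled comparison is confounded by the mix of anaesthetics. It is not. Randomisation balances the mix in expectation, and the simulated type I error stays near 5%. The trial calls itself pragmatic, so an all-patients comparison is a legitimate target. Pooling costs precision, not validity.

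Third, the plan already has a two-factor analysis, and it would be tempting to call ANOVA unsuited to a group piled at zero. As a blanket statement that is wrong: the additive model held its size and beat van Elteren at every share. The form does matter. With an interaction term, type I error for the arm effect rose to 9-20% at 60-70% spinal. Section 9.0 gives neither the outcome nor the form, labels the analysis sub-group, and the later Statistical analysis text omits it. It therefore does not repair the main comparison.

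Fourth, anaesthesia follows the block, and the anesthesiologist performing the block knows the allocation. If arm could influence the choice of anaesthetic, adjusting for the type actually given might introduce bias that the pooled test avoids. This stands, and it shapes the fix.

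Finally, the rank test applies only if normality fails. A cluster at zero beside a general-anaesthesia cluster would make that likely, and the t-test alternative is also unadjusted.

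**Conclusion.** The point holds in conditional form. Two secondary outcomes that may depend heavily on anaesthetic type are compared without accounting for it. If most spinal patients score zero in both arms, the pooled rank test gives up about 22 points of power at 30% spinal (65% v 87%), 32 at 50% (30% v 62%) and 25 at 60% (20% v 45%), under the effect assumed in step 4. If spinal patients score around 2-3, the loss is about 0-9 points. Stratifying was not materially worse in any setting examined.

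Some of the loss cannot be recovered, because spinal patients at zero carry little information: in step 5 even the stratified test falls from about 77% to 47% at 50% spinal. The documents do not support saying that power is halved as a matter of fact, or that the pooled result is invalid. The primary QoR-15 comparison and the 56 per arm are untouched. This is a worthwhile, inexpensive improvement to secondary analyses.

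**What to change.** 1. Add anaesthetic type to the variable list in section 6.0. Record the intended type before the allocation envelope is opened, for example at the presurgical evaluation, which the schedule lists ahead of randomisation. Record the type actually given as well.
2. In section 9.0 and the Statistical analysis text, pre-specify an anaesthetic-adjusted main comparison for immediate PACU VAS (rest and movement) and intraoperative opioid. Use either van Elteren stratified by general/spinal or an additive arm-plus-anaesthetic model, and name the choice in advance.
3. Report both outcomes by arm within general and within spinal anaesthesia, alongside the overall result.
4. State which outcomes the 2x2 ANOVA covers and in what form, and make the two statistical sections agree on it.

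The cost is one data item and some analysis wording, with no extra patients or visits. If only the type settled after allocation is available, the adjusted result needs a caveat that arm may have influenced it.

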 - Patient will be followed up until nerve block resolves.
 - Patients' participation in physical therapy will be recorded from physical therapy notes. Specifically, independence in mobility and transfers (independently, with minimal supervision, with moderate supervision, with maximal supervision) and ambulation distance will be recorded using standard PT protocols used at UAB Highlands.
 - The patients will be surveyed regarding their satisfaction with postoperative analgesia. Likert scale will be used to assess their satisfaction level. There will be 4 options to report: very unsatisfied, unsatisfied, satisfied, and very satisfied.
 - The hours from block placement until hospital discharge will be calculated.
- A blinded research associate will evaluate the patients postoperatively to collect data.

Procedure	Length of Time Required of Participants	Frequency of Repetition
Presurgical Evaluation on the day of surgery	30 minutes	once
Randomization on day of surgery	5 minutes	Once
Placement of block	Approximately 30 min.	Once
Post Anesthesia Care Unit (PACU) assessment	10 minutes	Once
First postoperative assessment survey (approximately 24 hours after surgery)	20 minutes	Once

Second postoperative assessment survey (approximately 48 hours after surgery)	10 minutes	Once
--	-------------------	-------------

- Measured Outcomes:

- Primary outcome:
 - Quality of Recovery after surgery assessed on postoperative day 1 (at 24 hours).
QoR-15 scale (form attached) will be used to assess post-operative recovery based on 15 questions: scores will range from 0-150, 0 being the worst recovery and 150 being the best (excellent) recovery.
- Secondary outcomes:
 - QoR-15 at 48 hours
 - VAS scores (0-10) at immediate postoperatively, 6, 12 and 24 hours at rest and movement. VAS score 0 indicates “no pain” and 10 indicates “worst pain experienced”. Highest pain score in first 24 hours will be recorded.
 - Opioid consumption intraoperatively, as well as at 24 hours postoperatively. Oxycodone PO and Hydromorphone iv usage in first 24 hours postoperatively.
 - Incidence of nausea, vomiting and itching in first 24 hours postoperatively.
 - Physical therapist assessment of independence in mobility and transfers (independent, with minimal supervision, with moderate supervision, with maximal supervision)

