 - Physical therapist documentation of ambulation distance
 - Patient satisfaction on Likert scale will be used to assess their satisfaction level. There will be 4 options to report: very unsatisfied, unsatisfied, satisfied, and very satisfied.
 - Hours to hospital discharge (Surgery finish time to discharge time).

List of variables/data points you will be collecting (e.g. – age, gender, date of surgery, etc.):

We will collect the following data:

1. patient age
2. patient gender

3. Weight
4. Height

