7.0 PLAN FOR STUDY: [Click here to enter text.](#)

- a. What is the potential impact of your study findings (e.g., how will findings impact clinical outcomes)? This study will compare the quality of recovery after total hip arthroplasty with PENG block for postoperative pain control versus no PENG block. The PENG block targets only the sensory branches and not the posterior mechanoreceptors; there is a potential motor-sparing effect which is desirable for early ambulation, better physical therapy, and earlier discharge. The effective analgesia and early ambulation provided by such regional anesthesia block may have positive impact on patient's mood, sleep, appetite and overall feeling of well-being. It remains unclear whether PENG block

provides sufficient analgesia and improves the quality of post-operative recovery after primary THA. .

- b. Do you plan to submit an abstract based on this project? Yes No (If yes, to which meeting venue? American Society of Regional Anesthesia
- c. Do you intend to publish the finding from this research project: Yes No

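### QoR-15 at 48 hours has no stated collection route after discharge and its planned test uses only completed forms; a model that also uses the 24-hour score would lose less

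*Combined protocol and SAP*

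**What the plan says.** Section 6.0 (data collected) states: "Quality of recovery (QoR) survey will be filled on post-operative day at 24 and 48 hours". The procedure table in the same section gives one ten-minute slot: "Second postoperative assessment survey (approximately 48 hours after surgery". Neither limits the survey to inpatients. Under Measured Outcomes, "QoR-15 at 48 hours" is the first secondary outcome; the 24-hour score is primary.

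On collection, section 6.0 says only: "A blinded research associate will evaluate the patients postoperatively to collect data". It names no telephone, electronic or take-home form and no time window. The one stated end of follow-up is "Patient will be followed up until nerve block resolves", which is tied neither to 48 hours nor to discharge.

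On discharge, section 7.0 (and the same sentence in section 2.0) says "there is a potential motor-sparing effect which is desirable for early ambulation, better physical therapy, and earlier discharge". Length of stay is part of the second objective in section 3.0, and section 6.0 lists "Hours to hospital discharge (Surgery finish time to discharge time" as a secondary outcome. No expected length of stay is given.

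On analysis, section 9.0 says "For data that are normally distributed, Student's t-test will be used to compare the groups", with a rank test for non-normal data. The closing Statistical analysis section, after the QoR-15 form, has the same pair of tests plus 95% confidence intervals. Neither section names an analysis set or a method for missing scores.

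**The concern.** The 48-hour comparison is the only planned look at whether a QoR-15 difference lasts beyond the primary time point. A two-sample test drops anyone without a 48-hour form. If forms are missed mainly because patients have gone home, the missing patients are likely to be the better recovered. If the block works as hoped, more of them will be in the block arm. The groups compared would then be smaller than planned and the block arm would look worse than it is. A reader could mistake that for a benefit fading by 48 hours. The 24-hour score, which carries information on the patients who left, is already collected but plays no part in the planned 48-hour test.

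**Working it through.** **1. The plan's own figure.** Inputs from section 9.0: difference 8, SD 15, 5% significance, 80% power. Two-sided:

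n = 2 × (1.960 + 0.842)² × 15² / 8² = 55.2, so 56 per group.

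This reproduces the stated 56 (a one-sided test would give 44). Exact t-test power at 56 per group is 79.9%. The figure is for 24 hours and has no allowance for missing scores. The plan states no effect or power for 48 hours; 8 points and SD 15 are carried over below as assumptions.

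**2. Fewer forms alone.** All loss rates are assumed. Each arm keeps 56 × (1 − loss) patients.

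| Loss, block / control | Patients left | Power for 8 points |
|---|---|---|
| 10% / 10% | 50 / 50 | 75% |
| 20% / 10% | 45 / 50 | 73% |
| 40% / 20% | 34 / 45 | 64% |
| 60% / 40% | 22 / 34 | 48% |

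**3. Bias by simple arithmetic.** Suppose leavers score d points above stayers in both arms, and a share m of an arm leaves. The stayers' mean is the arm mean minus m × d, so the bias in block minus control is −d × (m_block − m_control).

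- 20% / 10%, d = 5 to 15: −0.5 to −1.5 points.
- 40% / 20%, d = 5 to 15: −1 to −3 points.
- Equal loss: zero.

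**4. Simulation of the planned test against a model.** At least 4,000 trials per setting, 56 per arm. Both scores have SD 15 and a true difference of 8; the 24-hour control mean is 115 (the closing Sample size calculation cites 115 as a median). Assumed: correlation 0.6, and log-odds of leaving before 48 hours rising by 1 per SD of the 24-hour score. The block arm therefore loses more patients, because its 24-hour scores are 8/15 = 0.53 SD higher. The model is the likelihood estimator that uses the 24-hour score of every patient.

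| Controls gone before 48 h | Planned test: estimate, power | Model: estimate, power |
|---|---|---|
| 10% | 7.6, 72% | 8.0, 77% |
| 30% | 7.2, 54% | 8.0, 65% |
| 50% | 7.1, 39% | 8.0, 51% |
| 70% | 7.2, 24% | 8.0, 33% |

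The simulation standard error of a power near 50% is √(0.5 × 0.5 / 4000) = 0.8 percentage points. With no missing forms, both methods give about 80%.

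**5. Other assumptions.**

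- Weaker selection (0.5 per SD): planned-test estimate 7.7 to 7.9; power 75% / 61% / 45% / 28% at 10 / 30 / 50 / 70% gone.
- No selection: power 76% / 65% / 50% / 33%.
- Correlation 0.4, 50% gone: planned test 7.4 with 40% power; model 8.0 with 48%.
- An added direct effect of the block on discharge (+0.5 log-odds): planned test 6.5 to 6.6 with 42% to 43% power at 30% gone, and 6.2 to 6.4 with 27% at 50%. The model stays near 8.0, with 63% to 64% and 45% to 48%.
- Discharge driven by the 48-hour score itself, 30% gone: planned test 6.9, model 7.2. Both are biased, the model less.

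**The case against.** A reader might infer that the 48-hour test is bound to compare selected, unequal remainders of the arms. The documents do not support that. It needs a material share of patients home before 48 hours, their forms not obtained, and loss that is related to recovery and unequal by arm. None of these is stated. The survey is scheduled for every participant, so contact after discharge is unspecified, not excluded. Arrangements for it may also sit in consent or contact pages that are not in the text reviewed. Nor does the protocol expect earlier discharge in any quantified sense: it calls the motor-sparing effect potential and the earlier discharge desirable.

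Three further points have weight.

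- The bias is small. Without a direct effect on discharge it stays below 1 point when the 24-hour score drives leaving. Most of the power loss is simply fewer forms: at 50% of controls gone, power drops from 80% to 50% with no selection and to 39% with it.
- The model's unbiased 8.0 follows from letting only the 24-hour score and arm drive discharge. If later recovery drives it, the model is biased too, as step 5 shows.
- If every discharged patient is reached, the mixed model is not needed for this problem. The closing statistical section is in the past tense, so a change now may be post hoc.

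These points limit the claim but do not remove it. In every setting run with missing forms, the model had more power than the planned test and no greater bias, and with complete data the two agreed.

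**Conclusion.** The point holds in conditional form. The plan leaves open how the 48-hour QoR-15 is obtained after discharge, and its only analysis discards patients without that form. If forms are missed because patients went home, the comparison could lose a good deal of power and be modestly biased against the block. With 10% to 50% of controls gone, the planned test has about 72% to 39% power and an estimate of 7.6 to 7.1 against a true 8; the model has about 77% to 51% and 8.0. These figures rest on an 8-point effect and SD 15 holding at 48 hours, a correlation of 0.6, discharge driven by the 24-hour score, and an assumed share discharged. The missing route alone is a gap in detail. The stronger reason to act is that a better analysis is available from data already scheduled. The outcome is secondary, and the primary 24-hour comparison is not affected.

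**What to change.** 1. In section 9.0 and the closing Statistical analysis section, analyse 48-hour QoR-15 with a repeated-measures mixed model of the 24- and 48-hour scores: arm, time, arm-by-time, unstructured covariance, all randomised patients. Report the 48-hour contrast with its 95% confidence interval. Keep the planned t or rank test as a sensitivity analysis.
2. Report 48-hour completion by arm and by whether the patient had been discharged. Discharge time is already recorded.
3. If enrolment is open, state in section 6.0 that the blinded associate obtains the form by telephone or electronically after discharge.

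Cost: SAP wording, a short amendment, and a call of about ten minutes per discharged patient, which is the time already set aside for this survey. If enrolment is closed, only items 1 and 2 apply; they need no new data, and the model should be labelled post hoc if it is chosen after the data were seen. The downside is that the model assumes missingness depends on observed data. The primary analysis does not change.

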5. BMI
6. Surgical approach
7. ASA physical status
8. Average amount of opioids consumed daily in the week prior to surgery
9. VAS scores immediately postoperatively in the recovery room, 24 hours postoperatively
10. Opioid consumption intraoperatively and postoperatively
11. Physical therapy assessments
 1. Degree of independence in mobility and transfers at 24 hours
 2. Ambulation distance at 24 hours
12. Time to discharge from the hospital

Projected Overall Study Timeline

Date	Study Start-Up	Enrollment	Data Entry and Analysis	Study Write-Up
12 2020	X			
01 2021		X		
04 2021			X	
05 2021				X

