Data were summarised using means and standard errors (SE) for continuous outcomes or counts and percentages for categorical outcomes. Two-sample t-tests and chi-square tests were used to compare the two groups. Normality for continuous outcomes was assessed using probability plots and the Shapiro-Wilk test for normality. For any outcomes where normality could not be reasonably assumed, medians and interquartile ranges were reported instead of medians and standard errors, respectively, and the Wilcoxon rank sum test was used in place of the t-test. A 95% confidence interval for differences in means (for continuous outcomes) or relative risks (for categorical outcomes) were calculated. For any non-normally distributed continuous outcomes, asymptotic Hodges-Lehmann confidence limits were calculated.¹⁶ A p-value < 0.05 was considered statistically significant. SAS version 9.4 (SAS Institute Inc., Cary, NC) was used to conduct all statistical analyses.

Sample size calculation

A difference of 8 points is widely accepted as a minimal clinically important difference (MCID) for QoR-15 scores for perioperative interventions.¹⁷ A previous study showed a median QoR-15 score of 115 in the control group for the THA population.¹⁸ Assuming an increase to 123 in the QoR-15 score would be clinically relevant and a standard deviation of 15 points, we estimated that fifty-six patients were needed in each group for 80% power at a 5% significance level.

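### VAS pain is scheduled at four times, at rest and on movement, with only two-sample tests at 0.05 and no prespecified main pain comparison

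*Combined protocol and SAP*

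**What the plan says.** Section 6.0 lists among the secondary outcomes "VAS scores (0-10) at immediate postoperatively, 6, 12 and 24 hours at rest and movement". The data-collection text in the same section agrees: patients are seen in PACU and then at "6, 12 and 24 hours post-surgery to determine VAS pain scores at rest and movement on the scale of 0-10". A further pain variable is added: "Highest pain score in first 24 hours will be recorded".

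For continuous outcomes, section 9.0 (General Data Analysis Plan) says that for normal data Student's "t-test will be used to compare the groups", and otherwise: "For data that are not normally distributed, a Mann-Whitney tests will be used for comparisons". It sets p < 0.05 as the threshold for every comparison. The Statistical analysis text after the QoR-15 form says "Two-sample t-tests and chi-square tests were used to compare the two groups", with the Wilcoxon rank sum test for non-normal outcomes. It also provides 95% confidence intervals for mean differences, and Hodges-Lehmann limits where normality fails.

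The only ANOVA concerns anaesthesia type, not time: "The planned sub-group analysis will be conducted for GA vs. Spinal using a 2x2 ANOVA test". No repeated-measures model, key pain time point, testing order or multiplicity rule is given.

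The list of variables in section 6.0 names only "VAS scores immediately postoperatively in the recovery room, 24 hours postoperatively". The procedure table has a PACU assessment and surveys at about 24 and 48 hours, with nothing at 6 or 12 hours.

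**The concern.** Analgesia is the first item of the second objective (section 3.0), and section 2.0 says it is unclear whether the block relieves pain sufficiently. The plan does not say which comparison will answer that. With eight or nine results each eligible to be called significant, a report could lead with whichever time or condition crosses 0.05, and a reader could not tell whether it had been chosen in advance.

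Two lesser losses follow. A comparison at one time does not use the patient's other scores, so an effect sustained over the day is estimated less precisely than the data allow. A patient with one missing score also drops out of that comparison, although the other scores carry information. Separately, if the data forms follow the variable list or the procedure table, two of the four scheduled times could go uncollected.

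**Working it through.** **The plan's own figure.** Inputs from section 9.0: difference 8, SD 15, 5% significance level, 80% power. Taken as two-sided (the plan does not say), n per arm = 2 × (1.960 + 0.842)² × (15/8)² = 55.2, so 56. With the t distribution, 56 per arm gives 79.9% power. A one-sided calculation would give 44. The stated 56 is reproduced, and nothing below alters it.

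**Number of pain tests.** 4 times × 2 conditions = 8; the peak score makes 9.

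**Chance of at least one false positive if the block has no effect on pain.** Under independence this is 1 − 0.95^k:
- k = 8: 33.7%
- k = 9: 37.0%
- k = 4 (only the two times in the variable list, both conditions): 18.5%

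Scores from one patient are correlated, which lowers these figures. The documents give no correlation, so I assumed one common value ρ and simulated the eight tests at 56 per arm:

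| ρ (assumed) | 0.3 | 0.5 | 0.7 | 0.9 |
|---|---|---|---|---|
| At least one of 8 tests below 0.05 | 30% | 25% | 19% | 12% |

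In the same simulation one time-averaged contrast held its level, at 4.8% to 5.2%. With two times only (four tests), the figure is 16% at ρ = 0.5 and 13% at ρ = 0.7.

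**Precision of the time-averaged effect.** The variance of a four-time mean relative to a single score is (1 + 3ρ)/4. The effect profiles below are assumptions; power is for a two-sided t-test at 56 per arm.

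| ρ (assumed) | 0.3 | 0.5 | 0.7 |
|---|---|---|---|
| Variance ratio | 0.475 | 0.625 | 0.775 |
| Reduction in standard error | 31% | 21% | 12% |
| Power, constant 0.4 SD effect, average of four times | 86% | 76% | 66% |
| Power, 0.6 SD at the first two times and none later, average of four times | 63% | 51% | 43% |

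The comparators are one test at a single time: 55% for 0.4 SD, and 88% for 0.6 SD at an early time. In the second profile the mean effect is (0.6 + 0.6 + 0 + 0)/4 = 0.3 SD. Averaging therefore gains power when the effect lasts and loses it when the effect fades.

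**If rest and movement were both headline tests.** The chance of at least one false positive would be 1 − 0.95² = 9.75% under independence and about 8% at ρ = 0.7. This is why the fix names one condition.

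**The case against.** The strongest reply is that these are secondary outcomes. The trial has one primary outcome, QoR-15 at 24 hours, and without a multiplicity scheme the secondary p-values can be read as exploratory. That stands as far as the main conclusion goes. It does not supply a main pain comparison, and the plan attaches the word significant to every comparison at 0.05.

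A reader might infer several stronger criticisms that the documents do not support:
- *The tests are invalid because within-patient correlation is ignored.* A two-sample test at one time uses one value per patient, so each is valid. With complete data, a mixed model with unstructured covariance gives essentially the same contrast at a single time.
- *The plan has no overall pain measure.* The peak score in 24 hours is one value per patient over the whole window, and 24-hour opioid use is a related cumulative measure. Neither is named as the main analgesic comparison.
- *Only p-values will be reported.* The appended analysis text provides confidence intervals.
- *The plan states eight separate tests.* It gives general rules by data type. The eight follow because no other method for repeated scores is named.
- *The false-positive risk is one in three.* That needs independence, which is implausible for rest and movement scores in the same patient.
- *A repeated-measures analysis is always more powerful.* The block is a single preoperative injection, so a waning effect is plausible, and the working shows that the average can then do worse than one early test.

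The variable list is also plainly incomplete: it omits the QoR-15 itself. It does not prove that the 6- and 12-hour scores will be lost. But where it names VAS it gives two times only, and the procedure table has the same gap.

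**Conclusion.** The concern holds for the secondary pain outcome. The plan schedules eight VAS comparisons in the same patients, offers only two-sample tests at 0.05, and names no main one. The chance of at least one false positive among the eight is about 12% to 30% for assumed correlations of 0.9 to 0.3, or 2.4 to 6 times the nominal 5%; 34% is a ceiling under independence. The primary outcome's error rate and the sample size are untouched.

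The precision gain (standard error 12% to 31% lower at ρ = 0.7 to 0.3) belongs to the time-averaged effect. The matching power gain requires a roughly constant effect. Correlation, VAS standard deviation, effect profile and missing-data rate are not in the documents, so these figures are ranges under stated assumptions. The mismatch in pain assessment times is a real inconsistency within section 6.0. The change should be made, as an inexpensive improvement to how the analgesia claim can be read.

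**What to change.** 1. Analyse VAS on movement and VAS at rest each with one repeated-measures linear mixed model: arm, time and arm-by-time, with unstructured covariance.
2. Name one condition's overall 0-24 hour arm effect as the main pain comparison. Report the other condition, the time-specific differences with 95% confidence intervals and the peak score as supportive, without significance claims.
3. If scores are skewed or at the floor of the 0-10 scale, apply the planned rank-based test with Hodges-Lehmann limits to each patient's mean score as a sensitivity analysis.
4. Reconcile the variable list and the procedure table with the 6- and 12-hour assessments in the data-collection and outcome text, so that the model has its data.

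The cost is a few lines of analysis text and one mixed-model procedure in SAS, which the plan already uses. The statistical price is dilution of an effect confined to the early hours; the time-specific estimates from the same model would show it. The appended analysis text is in the past tense. If the pain data have already been analysed, the new main comparison must be labelled post hoc.
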